11.1.2 Disease Parameters

Target lesions. All lesions which are visible on imaging prior to SBRT and are targets for radiotherapy will be considered target lesions and should be recorded and measured at baseline.

Non-target lesions. Any metastatic lesions that arise in follow-up imaging after completion of radiotherapy which were not target lesions for the initial radiotherapy. These sites of relapse are not required to receive treatment with SBRT, but may be treated at the discretion of the treating clinician. The treatment may be palliative or locally aggressive, and is not subject to the guidelines of the radiation treatment parameters described in section 6.

11.1.3 Methods for Evaluation of Disease

All measurements should be taken and recorded in metric notation using a ruler or calipers. All baseline evaluations should be performed as closely as possible to the study enrollment and treatment and never more than 4 weeks before study enrollment.

The same method of assessment and the same technique should be used to characterize each identified and reported lesion at baseline and during follow-up. Imaging-based evaluation is preferred to evaluation by clinical examination when both methods have been used to assess the antitumor effect of a treatment.

Clinical lesions: Clinical lesions will only be considered measurable when they are superficial (e.g., skin nodules and palpable lymph nodes). In the case of skin lesions, documentation by color photography, including a ruler to estimate the size of the lesion, is recommended.

Conventional CT and MRI: These techniques should be performed with cuts of 5 mm or less in slice thickness contiguously. Spiral CT should be performed using a ≤ 5 mm contiguous reconstruction algorithm. This applies to tumors of the chest, abdomen, and pelvis. Head and neck tumors and those of extremities usually require specific protocols.

11.1.4 Response Criteria

11.1.4.1 Evaluation of Target Lesions will occur to determine lesion control at each CT scan evaluation. Local control will be defined as the lack of progressive disease based on the criteria below:

Complete Response (CR):	Disappearance of target lesion
Partial Response (PR):	At least a 30% decrease in the sum of the longest diameter (LD) of target lesion, taking as reference the baseline sum LD
Progressive Disease (PD):	At least a 20% increase in the sum of the LD of target lesion, taking as reference the smallest sum LD recorded since the treatment
Stable Disease (SD):	Neither sufficient shrinkage to qualify for PR nor sufficient increase to qualify for PD, taking as reference the smallest sum LD since the treatment started

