3. PATIENT SELECTION

3.1 Eligibility Criteria

- 3.1.1 Patients must have histologically or cytologically confirmed metastatic or recurrent RCC (any histologic subtype).
- 3.1.2 Patients must have between 1 to 5 new or recurrent lesions suspicious for metastatic RCC on diagnostic imaging.
 - 3.1.2.1 Each extracranial lesion must be ≤ 6 cm and amenable to SBRT or surgical excision.
 - 3.1.2.2 Patients must have 3 or fewer brain metastases, of size ≤ 4 cm.
 - 3.1.2.2.1 Brain metastases must be treated prior to enrollment in the study. The modality of treatment of brain metastases can include surgical resection, whole brain radiotherapy, stereotactic radiosurgery, or any combination of the above.
 - 3.1.2.3 Patients who have an intact unresected primary tumor should be considered for radical nephrectomy and primary resection prior to enrollment in the study. If the patient is not eligible for surgical resection, the primary tumor must be amenable to SBRT or RFA. Generally, this will be defined as a primary tumor <10 cm in size or a primary lesion which can be treated to a dose of ≥ 8 Gy x 5 without excessive perceived risk of toxicity.
- 3.1.3 Patients must have had at least a CT of the chest, abdomen, and pelvis within 4 weeks of registration in the trial. CT or MRI of the brain is only required in the presence of neurologic symptoms.
- 3.1.4 Patients must have had no radiotherapy, immunotherapy, chemotherapy or therapy with targeted agents within the last 1 month.
- 3.1.5 Patients may not have had prior bevacizumab, based on case reports of tracheo-esophageal fistula in patients treated with bevacizumab and radiotherapy [58, 59].
- 3.1.6 Age ≥ 18 years. Because of the risk of adverse events in patients <18 years of age, children are excluded from this study, but will be eligible for future pediatric SBRT trials.

- 3.1.7 ECOG performance status ≤ 2 (see Appendix A).
- 3.1.8 Life expectancy of ≥ 3 months.
- 3.1.9 Patients must have normal organ and marrow function within 30 days of registration, as defined below:
- absolute neutrophil count $\geq 500/\text{mcL}$
 - hemoglobin $\geq 8.0 \text{ g/dL}$
 - platelets $\geq 50,000/\text{mcL}$
 - total bilirubin within normal institutional limits
 - AST(SGOT)/ALT(SGPT) $\leq 3X$ institutional upper limit of normal if liver metastases are present
- 3.1.10 Women of childbearing potential must have a negative pregnancy test within 14 days of registration.

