7.1.3 Additional Adverse Events Associated with Lung/Mediastinal Radiation

Acute Reactions: Cough and esophagitis (if the esophagus is included in the radiation therapy portal) are likely. Severe esophagitis (requiring IV hydration, therapy interruption, or severe cough), shortness of breath, and hemoptysis are possible but less likely.

Late Reactions: Asymptomatic fibrotic changes in the lung seen on chest imaging are likely. Severe pneumonitis or fibrosis of lung resulting in severe respiratory compromise, symptomatic esophageal stricture, radiation pericarditis, and myocardial injury, spinal cord injury, and brachioplexopathy are possible but unlikely side effects of radiation.

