11.1.5 Endpoint Definitions

Duration of treated lesion control

Duration of time from start of treatment to the time of local progression at each treated lesion. Local progression is defined as any progressive disease as judged by RECIST criteria of treated lesions

Organ-specific control

Duration of time from start of treatment to the time of development of a new lesion on imaging within an organ in which a lesion was treated with SBRT.

Progression-free survival

Duration of time from start of treatment to time of progression. Progression is defined as any new sites of disease on imaging or any progressive disease by RECIST criteria at initially treated sites of disease (within 80% isodose line).

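### Progression at a treated lesion needs only a 20% rise in diameter, with no minimum growth in millimetres, so in lesions below 25 mm measurement noise can be scored as local failure

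*Combined protocol and SAP*

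**What the plan says.** Section 11.1.2 (Disease Parameters) decides which lesions are followed: "All lesions which are visible on imaging prior to SBRT and are targets for radiotherapy will be considered target lesions". It gives no lower size limit. The size limits in section 3.1 are all upper limits, for example "Each extracranial lesion must be ≤ 6 cm and amenable to SBRT or surgical excision".

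Section 11.1.4.1 sets the timing, "Evaluation of Target Lesions will occur to determine lesion control at each CT scan evaluation", and the progression threshold, "At least a 20% increase in the sum of the LD of target lesion, taking as reference the smallest sum LD recorded".

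Section 11.1.5 turns the reading into an event: "Local progression is defined as any progressive disease as judged by RECIST criteria of treated lesions". The same reading at a treated site, within the 80% isodose line, is also a PFS event.

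The Study Summary Schema and the section 10 calendar give imaging at 3, 6, 9 and 12 months. The synopsis (Statistical Methods) plans 1-year Kaplan-Meier estimates of LeC and PFS. Section 12.5 adds a descriptive comparison of each lesion's dose with its local control.

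**The concern.** A purely proportional threshold becomes very small in millimetres when the lesion is small. Comparing each scan with the smallest earlier value makes this worse, because a low reading becomes the reference for every later scan, and each further scan is another chance to cross the line. A lesion that has shrunk is exposed in the same way, since its reference is now small.

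False local failures would lower 1-year LeC and PFS, distort patterns of failure and add noise to the dose comparison. Section 2.4 says the results should help with sample size calculations for later trials. With at most 25 patients, a few misclassified lesions could move these estimates visibly.

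**Working it through.** **The plan's own figure.** The plan states no operating figure for LeC or PFS. Its one power figure, 78.8% for the toxicity rule (section 12.1), reproduces: an exact binomial recursion with boundaries 2 in 2, 3 in 14 and 4 in 25 gives 78.84% at a true rate of 20%. This point does not touch it.

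**Growth needed.** Required growth = 0.20 × reference diameter.

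- 10 mm: 2 mm
- 15 mm: 3 mm
- 20 mm: 4 mm
- 25 mm: 5 mm
- 30 mm: 6 mm
- 60 mm: 12 mm

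The rule demands 5 mm or more only from 5 / 0.20 = 25 mm upward.

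**One comparison.** Let a stable lesion of true diameter d be read with independent normal error of SD s. The first follow-up reading is at least 1.2 times baseline with probability 1 − Φ(0.2d / (s√(1 + 1.2²))). For d = 10 mm and s = 1 mm this is 1 − Φ(2 / 1.562) = 1 − Φ(1.28), about 10%, at the first scan alone.

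**Four scans.** Simulation of 400,000 stable lesions per setting, with one baseline and four follow-up readings. Progression is a rise of at least 20% over the smallest earlier reading, baseline included. The SD is an assumption, so a range is shown. Entries are the chance of at least one false progression.

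| True diameter | SD 0.5 mm | SD 1.0 mm | SD 1.5 mm | SD 2.0 mm |
|---|---|---|---|---|
| 10 mm | 4% | 50% | 74% | 85% |
| 15 mm | 0.1% | 18% | 50% | 69% |
| 20 mm | 0% | 4% | 27% | 50% |
| 30 mm | 0% | 0.1% | 4% | 18% |
| 10 mm, with a 5 mm minimum added | 0% | 0.2% | 7% | 25% |

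If baseline is left out of the reference, the 10 mm figures at SD 0.5, 1.0 and 1.5 mm are 3%, 37% and 61%. A lesion that shrinks from 20 to 10 mm by the first scan and then stays stable has a 37% chance at SD 1.0 mm.

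**Next-scan confirmation.** At 10 mm, confirmation without a 5 mm minimum leaves 0.4%, 15% and 33% at SD 0.5, 1.0 and 1.5 mm. With both rules it leaves 0%, 0% and 0.6%. The price is missed real failures. Take a lesion that truly grows from 10 to 17 mm by 12 months, with SD 1.0 mm. On a straight-line path, the 5 mm rule alone calls progression about 95% of the time, and both rules together about 58%. If growth starts only after 6 months (13.5 mm at 9 months), the figures are about 99% and 30%.

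**The case against.** **The plan adopts a published standard.** Section 11.1 cites RECIST and refers to patients with measurable disease. If the cited guideline sets a minimum measurable size, small lesions might be excluded by reference. The documents state no such size for CT or MRI, and section 11.1.2 counts every irradiated lesion. This softens the point without removing it.

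**The rates rest on an assumed SD.** This stands. At 0.5 mm the problem is small even at 10 mm, and at 30 mm it is 4% or less up to an SD of 1.5 mm. The documents give no distribution of lesion sizes, so the effect on the trial's LeC estimate cannot be calculated. A reader might take the slice limit in section 11.1.3, "These techniques should be performed with cuts of 5 mm or less in slice thickness contiguously", as proof of large error. It is an upper limit, and slice thickness is weak evidence about error in an in-plane diameter. The same section also asks for the same technique at every assessment.

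**Fibrosis.** Section 7.1.3 says "Asymptomatic fibrotic changes in the lung seen on chest imaging are likely", and a reader might infer that fibrosis will be counted as progression. The documents do not say that it enlarges a lesion's measured diameter. Nor would a 5 mm minimum or a repeat scan settle the matter: section 7.1 defines late reactions as those beyond 90 days, and lasting fibrosis would still be there three months later.

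**Reference scan.** The progression row dates its reference from the treatment, while the stable-disease row dates it from the start of treatment. A reader might infer that baseline is excluded, so that a lesion growing from 30 to 40 mm at the first scan would then need 40 × 1.2 = 48 mm. A dropped word is the likelier explanation. This is an ambiguity to close, not a demonstrated error.

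**Secondary endpoints only.** This is true. Section 11.1 says response is not the primary endpoint, and section 12.5 plans descriptive analysis without formal testing.

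**Conclusion.** The point holds as an inexpensive improvement to secondary endpoints. Below a reference diameter of 25 mm the rule accepts growth of less than 5 mm, and no other section adds a size minimum, an absolute increase or a check on the reading. For a stable 10 mm lesion the chance of a false failure within the year runs from about 4% to 74% as the assumed SD goes from 0.5 to 1.5 mm. It falls quickly as lesions get larger. The figures also assume independent normal errors and all four scans done.

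The documents support saying that noise can be scored as failure. They do not support saying that it will be, that lung lesions are mainly affected, or that fibrosis is misread as tumour at any particular rate. The primary toxicity endpoint, sample size and stopping rule are unchanged.

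**What to change.** In section 11.1.4.1, define progression at a treated lesion as an increase of at least 20% and at least 5 mm in that lesion's longest diameter over the smallest value on study, and state that the baseline scan counts. Point the LeC and PFS definitions in section 11.1.5 to this wording. Report LeC and PFS under the existing 20% rule as a sensitivity analysis.

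Use next-scan confirmation only as a further sensitivity analysis. It can miss real late failures, and it cannot confirm progression first seen at 12 months.

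The cost is wording, applied to scans already scheduled. The definition governs endpoint scoring only, not patient care. The downside is later calling of true failure in small lesions: a 10 mm lesion must reach 15 mm (50% growth) instead of 12 mm, and a 5 mm lesion must double. Reporting the 20% rule alongside shows how much this matters. How lasting fibrosis is told apart from regrowth remains a separate question, which the sponsor should answer in the protocol.

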11.1.4.2 Evaluation of Non-Target Lesions

By definition, the appearance of new non-target lesions following completion of radiotherapy will be considered overall progressive disease.

If for any reason the response of non-target lesions to systemic therapy is needed, the same criteria as those for target lesions will be used for Complete Response, Partial Response, Progressive disease, and Stable disease for each individual non-target lesion during follow-up evaluations.

11.1.5 Endpoint Definitions

Duration of treated lesion control

Duration of time from start of treatment to the time of local progression at each treated lesion. Local progression is defined as any progressive disease as judged by RECIST criteria of treated lesions

Organ-specific control

Duration of time from start of treatment to the time of development of a new lesion on imaging within an organ in which a lesion was treated with SBRT.

Progression-free survival

Duration of time from start of treatment to time of progression. Progression is defined as any new sites of disease on imaging or any progressive disease by RECIST criteria at initially treated sites of disease (within 80% isodose line).

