Definition of primary outcome/endpoint: RT-related grade ≥ 4 toxicity will be determined on a case-by-case basis by the study group, taking into consideration the region treated with SBRT, timing of the toxicity, and the nature of the toxicity. Toxicities will be graded as per CTCAE v4.0 criteria.

Definition of secondary outcomes/endpoints: LeC will be defined as absence of clinical or radiographic progression per RECIST criteria. PFS will be defined as progression in the treated lesion, organ in which the treated lesion is present, distant failure, or death from any cause.

Analytic plan for primary objective: Rates of RT-related grade ≥ 4 toxicity will be recorded, time to RT-related grade ≥ 4 toxicity will be recorded, and freedom from RT-related grade ≥ 4 toxicity will be determined using the Kaplan-Meier method.

Analytic plan for secondary objectives: LeC and PFS will be estimated at 1 year using the Kaplan-Meier method.

Sample size justification: A sample size of 25 patients will be needed to assess the safety and appropriateness of this method, identify the optimal candidates, and optimal SBRT fractionation/dose for different clinical scenarios.

TABLE OF CONTENTS

	Page
SCHEMA	i
1. OBJECTIVES	1
1.1 Primary Objectives	1
1.2 Secondary Objectives	1
2. BACKGROUND	1
2.1 Metastatic Renal Cell Carcinoma	1
2.2 Oligometastasis	1
2.3 Stereotactic Body Radiotherapy in Oligometastasis	2
2.4 Rationale for current study	3
2.4.1 Rationale for Secondary Objectives	4
3. PATIENT SELECTION	4
3.1 Eligibility Criteria	4
3.2 Exclusion Criteria	5
3.3 Inclusion of Women and Minorities	6
4. REGISTRATION PROCEDURES	6
4.1 Patient Recruitment	6
4.2 Patient Renumeration	6
5. TREATMENT PLAN	6
5.1 Study Design	6
5.2 Definition of Grade ≥ 4 RT-related Toxicity	6
5.3 General Concomitant Medication and Supportive Care Guidelines	7
5.4 Duration of Therapy	7
5.5 Duration of Follow Up	7
5.6 Criteria for Removal from Study	7
6. RADIATION THERAPY	7
6.1 Simulation	7
6.2 Premedications	8
6.3 Target Volumes	8
6.4 Treatment Planning	8
6.5 Dose Specifications	8
6.6 Critical Structures	9
6.7 RT Treatment	13
6.8 Radiotherapy Adverse Events	13
7. RISKS AND BENEFITS	13
7.1 Radiotherapy Adverse Events	13
8. Adverse Event Reporting	15
9. Data Safety Monitoring	16
10. STUDY CALENDAR	16
11. MEASUREMENT OF EFFECT	17
11.1 Antitumor Effect and Endpoints	17
11.2 Dosimetric description of delivery of Radiotherapy	18
12. STATISTICAL CONSIDERATIONS	19
12.1 Study Design/Endpoints	19

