2.3 Stereotactic Body Radiotherapy in Oligometastasis

However, nephrectomy and metastasectomy are invasive procedures with risk for perioperative morbidity. This is particularly the case for patients having comorbid conditions or requiring more extensive surgeries. Also, not all patients are candidates for resection due to invasion of adjacent structures by tumors. Radiotherapy is an alternative modality used for the treatment of radiographically visible tumors. Although RCC has historically been thought to be resistant to conventionally fractionated radiotherapy (1.8-2 Gy per fraction) [32-34], multiple series suggest it may be sensitive to higher fraction sizes of radiotherapy (stereotactic radiotherapy) [35-38].

Stereotactic Radiotherapy is the use of high doses of radiation per fraction to deliver ablative doses of radiation to lesions throughout various body sites. Stereotactic radiotherapy administered in one fraction, commonly to intradural lesions, is usually described as stereotactic radiosurgery (SRS). Stereotactic radiotherapy administered over 1-5 fractions to extracranial sites in > 5 Gy per fraction is known as stereotactic body radiotherapy (SBRT).

There is considerable experience with SBRT in medically inoperable early stage lung

cancers [39-42], and an increasing body of evidence suggesting a role of SBRT in oligometastatic cancers. The ablative doses of SBRT in the oligometastasis setting have allowed for local control rates approaching 90% in such series [43-46].

Based on retrospective series suggesting a local control rate with SBRT of 87-98% [35, 47-49], a prospective Phase II Swedish study assessed the role of SBRT in 30 patients with metastatic or inoperable primary tumor RCC [38]. Patients were treated with 20-50 Gy given in 2-5 fractions to involved sites. With median follow-up of 52 months, 21% of patients had complete regression of tumor, 31% had a partial response, and 27% had stable radiographic size. The rate of local control for all treated lesions was 98%, and the overall survival for the entire cohort was 32 months. This suggests SBRT can be effective to control RCC. Additionally, retrospective series also suggest limited toxicity with SBRT [37, 45, 47, 49-51].

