6.5 Dose Specifications

Doses will be prescribed to the PTV. The PTV may be covered by a lower isodose line than usually used in conventional radiotherapy planning, ranging from 60-100%. Ideally, the prescription dose will cover $>90\%$ of the GTV ($V_{100} \text{ GTV} > 90\%$, and $V_{95} \text{ PTV} > 90\%$). Hot spots within the PTV are allowed, unless the PTV also overlaps an organ at risk. A lower coverage goal will be acceptable if necessary to meet normal tissue constraints, which will be assigned priority over tumor coverage.

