12.5 Analysis of Secondary Endpoints

The secondary endpoints of this study include determining the toxicity profile, LeC, and patterns of failure of this approach, as well as the feasibility of a 5-fraction SBRT regimen based on normal tissue dose constraint and treatment goals, and the feasibility of accrual to an oligometastasis trial in RCC and adequacy of the eligibility criteria.

A database will be created that is HIPAA compliant to store the information to perform analyses. A unique study number will be assigned to each patient that will be used for all analyses. Variables will be defined as described in section 11. The results of analyses will be described but no formal statistical analysis will be performed.

Grade ≥ 4 RT-related toxicities will be recorded in database and are described as in section 5.2. The ultimate allocation of a toxicity as RT-related or non-RT-related will be decided by the study committee. Toxicities of interest that occur within the 3-12 month time frame after RT start will be documented and analyzed using descriptive statistics.

The durations of treated lesion control, organ-specific control, distant metastasis free survival, progression-free, overall and cause specific survival as defined in section 11.1.5 will be calculated for each patient. Descriptive statistics will be used to estimate these secondary endpoints using the Kaplan-Meier method (secondary aims 1.2.1, 1.2.3).

The radiotherapy doses for each treated site will be recorded. The doses to the

corresponding normal tissues will also be recorded. The maximum dose to each site while staying within dose constraints will be described. The dose to each lesion will also be compared to the local control of the corresponding lesion and described.

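### PFS is defined twice, once with death as an event and once without, and the analysis section points to the version without

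*Combined protocol and SAP*

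**What the plan says.** The synopsis, under the definition of secondary endpoints, makes PFS end at "progression in the treated lesion, organ in which the treated lesion is present, distant failure, or death from any cause". Beside that definition it plans the analysis: "LeC and PFS will be estimated at 1 year using the Kaplan-Meier method".

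Section 11.1.5 gives a different definition: "Duration of time from start of treatment to time of progression. Progression is defined as any new sites of disease on imaging". It then names a second kind of event, which it confines to the irradiated area: "any progressive disease by RECIST criteria at initially treated sites of disease (within 80% isodose line"). Death does not appear.

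Section 12.5 takes its variable definitions from Section 11 and states that "progression-free, overall and cause specific survival as defined in section 11.1.5 will be calculated for each patient". It uses Kaplan-Meier but names no time point. No section says whether the synopsis or the body prevails, and none says how a patient who dies without documented progression is handled.

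**The concern.** Two analysts working from different sections could report different 1-year PFS figures from the same 25 patients, and both could claim to have followed the plan. The one who follows 12.5 to 11.1.5 treats a death without documented progression as a non-event. The estimate is then time to progression under a name that readers take to include death, and any error runs in the favourable direction.

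Such deaths are possible here. The eligibility criteria admit ECOG 2 and a life expectancy of only three months, and follow-up imaging is three-monthly, so a patient can die between scans.

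The definitions also differ on treated sites. Section 11.1.5 limits progression there to the 80% isodose line, without saying whether that means 80% of the prescribed or of the maximum dose. Section 6.5 adds to the uncertainty: "The PTV may be covered by a lower isodose line than usually used in conventional radiotherapy planning, ranging from 60-100" per cent. The synopsis has no such limit.

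The stake is modest but real. PFS is a named secondary objective, and Section 2.4 expects the pilot's data to inform sample sizes for later trials.

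**Working it through.** The plan states no figure for PFS, so there is none to reproduce. Its only power figure, 78.8% for the toxicity boundary in Section 12.1, reproduces (78.84% by exact recursion at a 20% toxicity rate) and does not involve PFS.

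**The texts side by side**

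| | Synopsis | Section 11.1.5 |
|---|---|---|
| Death from any cause | Event | Not named |
| Progression at treated site | No spatial limit | RECIST, within 80% isodose line |
| New disease | Treated organ or distant | Any new site on imaging |
| Analysis attached | Kaplan-Meier at 1 year | Kaplan-Meier through 12.5, no time point |

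**Step 1: exact Kaplan-Meier counts.** Inputs: n = 25 (Section 12.2) and 1 year of follow-up (Section 5.5). Assumptions: 12 progressions, d deaths without documented progression, no other censoring before 1 year. No censoring rule is written, so treating these deaths as censored under 11.1.5 is an inference.

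- Deaths counted: (25 − 12 − d)/25
- Deaths censored, all before the first progression: (25 − d − 12)/(25 − d)
- Deaths censored, all after the last progression: (25 − 12)/25

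| d | Counted | Censored, early | Censored, late | Gap (points) |
|---|---|---|---|---|
| 0 | 13/25 = 52.0% | 52.0% | 52.0% | 0 |
| 1 | 12/25 = 48.0% | 12/24 = 50.0% | 13/25 = 52.0% | 2.0 to 4.0 |
| 2 | 11/25 = 44.0% | 11/23 = 47.8% | 13/25 = 52.0% | 3.8 to 8.0 |

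With 10 progressions assumed instead, one death gives 14/25 = 56.0% against 14/24 = 58.3% to 15/25 = 60.0%, again about 2 to 4 points.

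**Step 2: expected overstatement.** Let S be the assumed 1-year progression-free proportion ignoring deaths, and q the net 1-year risk of death without progression, with independent constant hazards. PFS is S(1 − q), so the overstatement is S × q.

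| S | q = 5% | q = 10% |
|---|---|---|
| 0.30 | 1.5 points | 3.0 points |
| 0.50 | 2.5 points | 5.0 points |
| 0.70 | 3.5 points | 7.0 points |

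At S = 0.50 the progression hazard is 0.693 per year. The expected number of such deaths in 25 patients is:

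- q = 5%: 25 × [0.051/(0.693 + 0.051)] × (1 − 0.50 × 0.95) = 0.9
- q = 10%: 25 × [0.105/(0.693 + 0.105)] × (1 − 0.50 × 0.90) = 1.8

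**Step 3: is 5 to 10% plausible?** The documents give no rate for these deaths. Section 2.3 reports of a prior SBRT study that "the overall survival for the entire cohort was 32 months". If that is a median with constant hazard (both assumptions), the hazard is ln 2 × 12/32 = 0.2599 per year, a 1-year mortality of 22.9%. The share of that hazard which progression-free patients would need is:

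- q = 5%: 0.0513/0.2599 = 20%
- q = 10%: 0.1054/0.2599 = 41%
- q = 20%: 0.2231/0.2599 = 86%, which is why 20% is left out of the main range

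**Step 4: scale.** The binomial standard error at 50% with n = 25 is √(0.5 × 0.5/25) = 10 points.

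**The case against.** The strongest reply is that the plan does choose: 12.5 is the operative analysis section and it names 11.1.5. That is true of 12.5's own analysis. But the version it selects omits death, and the synopsis keeps a separate 1-year PFS plan tied to the other definition. The conflict remains.

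A second reply is that 11.1.5 is silent on death rather than excluding it, so an analyst might count deaths by convention. That is possible, and it means every figure above depends on a literal reading. A definition that relies on the analyst ignoring its wording still needs correcting.

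A third is that the isodose limit may only separate in-field progression from new disease, since 11.1.5 also counts new sites. That may be the intent, but the text does not say so. The zero difference without deaths therefore covers death handling only. The limit could remove some events as well, and that effect is not quantified here.

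A fourth is that the size rests on assumed rates. This stands, and the upper end depends on the survival anchor. Section 2.1 cites medians of 6 to 15 months for metastatic disease generally. At 15 months the hazard is ln 2 × 12/15 = 0.5545, and a 20% risk needs only 0.2231/0.5545 = 40% of it. The overstatement at S = 0.50 would then be 10 points, so 5 to 10% is not a ceiling.

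Finally, the impact is small: a descriptive secondary endpoint, with a gap for one or two such deaths below the 10-point standard error. That stands and limits the weight of the point. Deaths would still be seen in overall and cause-specific survival and, if RT-related, in the primary endpoint. However, 12.5 refers to 11.1.5 for those two survival endpoints, and 11.1.5 defines neither.

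**Conclusion.** The concern holds. The two PFS definitions conflict in the current text, and a literal reading of 12.5 yields time to progression labelled as PFS. The error is in one direction: the 11.1.5 figure is at or above PFS with deaths counted. Under the assumptions stated (25 patients, 12 progressions, full follow-up, deaths censored), it is 2.0 to 4.0 points for one death without documented progression and 3.8 to 8.0 for two. In expectation it is 2.5 to 5 points at 50% progression-free with a 5 to 10% death risk, and 1.5 to 7 points across 30 to 70%. From death handling alone it is zero if no such death occurs. No stopping rule, power or sample size depends on PFS. This should be corrected, but it does not threaten the trial's main conclusion.

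**What to change.** State one definition, in identical words, in the synopsis and in 11.1.5: time from start of SBRT to the first of a new site of disease, RECIST progression at a treated site, or death from any cause. Add that patients alive and progression-free are censored at their last disease assessment. Say whether the 80% isodose limit applies to treated-site progression and, if it does, 80% of which dose. If the present 11.1.5 quantity is wanted, call it time to progression and report it separately. In the same edit, carry the synopsis's 1-year time point into 12.5 and define the overall and cause-specific survival that 12.5 attributes to 11.1.5.

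The cost is a short wording change, with no new data, visits or patients. The reported PFS may come out slightly lower.
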